Patients will be treated in 28-day cycles. Patients who discontinue treatment for progressive disease and/or use of other CLL/SLL therapy will be followed for survival every 24 weeks (± 7 days) for up to 3 years. Patients who discontinue treatment for reasons other than progressive disease, use of other CLL/SLL therapy, death, or withdrawal of consent will have response assessments every 12 weeks (± 7 days) until progressive disease occurs. Thereafter they will be followed for survival every 24 weeks (± 7 days) for up to 3 years. All patients will discontinue survival follow-up upon completion of 3 years of survival follow-up, withdrawal of consent, death, or study closure, whichever is the earliest.

Cohort A1 will follow a conventional "3+3" patient enrollment scheme for the dose escalation part of the study. Patients will be dosed with MS-553 by mouth twice daily at an initial dose (dose level 0, DL 0) of 100 mg BID daily in 28-day cycles. MS-553 shall be taken with food.

Dose Level	Dose
0	100 mg BID
1	200 mg BID
2	250 mg BID
3	300 mg BID
4+	TBD* mg BID

*To be determined

After completion of dose level 3 (DL 3), the dose escalation of MS-553 can continue in 50 mg BID increments (or lower if an intermediate dose is introduced) until a MTD is reached. Or, the Safety Review Committee and/or the Sponsor may declare an initial RP2D, if further dose escalation is not warranted prior to reaching MTD. Furthermore, in order to facilitate initial RP2D determination, select cohort(s) may be expanded up to 10 patients total in a cohort to assess the safety and clinical activity of MS-553 provided that the dose does not exceed the MTD and the Safety Review Committee, upon reviewing the safety and tolerability, efficacy, and available PK and PD data, agrees.

During the dose escalation period, intra-patient dose escalation will be permitted at the discretion of the study investigators and after discussion with the medical monitor and Sponsor, if the following criteria are met:

1. The next higher dose for the regimen has been demonstrated to be safe by at least 3 patients and all 3 patients complete one cycle without experiencing any dose limiting toxicity (DLT).

- 2. The patient who will receive the higher dose has not experienced a DLT and has also completed at least 2 cycles of therapy at the current dose.
- 3. Intra-patient dose escalation can be increased by only one dose level at a time.

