Initial RP2D of MS-553 for the combination is expected to be reached before the dose escalation reaches 250 mg BID, the high dose level of MS-553 under testing as monotherapy. Intermediate dose levels (i.e. at 25 mg increment) or even lower dose levels may also be evaluated as determined by the Investigators, the Safety Review Committee and Sponsor until the MTD or initial RP2D for the combination is determined.

Cohort C2. After the MTD or initial RP2D is identified for the combination of MS-553, venetoclax and rituximab, an expansion cohort of approximately 20 patients will be initiated. Treatment experienced CLL/SLL patients, eligible for standard of care venetoclax and rituximab, who are naïve to prior Bcl-2 inhibitor treatment and who have had no more than 2 prior lines of treatment regimens are eligible for this cohort to further confirm the safety of the combination and assess early evidence of anti-tumor activity. Venetoclax will be initiated on Cycle 3 following the administration of MS-553 and rituximab combination for two cycles. For this reason, the DLT evaluation period for the triplet combination is extended to 4 cycles of therapy in order to include ramping up of the venetoclax dose that is introduced in Cycle 3.

Patients in Cohort C1 and C2

Patients will be treated in 28-day cycles provided they continue to tolerate the drug, have no evidence of progression, and do not meet any of the criteria for discontinuation. All patients will continue to be monitored for approximately 30 days (+7 days) after treatment discontinuation for development of any late treatment emergent adverse events. Any adverse events noted during the DLT evaluation periods will be considered in the determination of the maximum tolerated dose/initial RP2D and dose schedule to be taken forward into the expansion phase of the study.

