During the dose escalation period, intra-patient dose escalation will be permitted at the discretion of the study investigators and after discussion with the medical monitor and Sponsor, if the following criteria are met:

- The next higher dose for the regimen has been demonstrated to be safe by at least 3 patients and all 3 patients complete one cycle without experiencing any DLT.
- 2. The patient who will receive the higher dose has not experienced a DLT and has also completed at least 2 cycles of therapy at their current dose.
- 3. Intra-patient dose escalation can be increased only by one dose level at a time.

After completion of each dose escalation cohort, the SRC will review clinical safety and tolerability data as well as PK data available at the time for all patients in order to confirm dose escalation to the next dose level. Based on the SRC's review, a cohort may be expanded, or an intermediate or a lower-than-planned dose level or an alternative dosing schedule may be evaluated.

All patients will continue to be monitored for approximately 30 days (+7 days) after treatment discontinuation for development of any late treatment emergent adverse events. Any such late adverse events will be considered in the determination of the MTD/initial RP2D and dose schedule to be taken forward into the expansion phase of the study.

While the

MTD was not reached, an initial RP2D was identified. **Second Second** the SRC reviewed all available efficacy, safety, PK and PD data of Cohort A1 and some Cohort A2 patients and agreed on an updated RP2D with a ramp-up dosage regimen as shown in Table 3 below.

MS-553	Oral Daily Dose
Weeks 1 to 4 (Cycle 1)	150 mg BID
Weeks 5-8 (Cycle 2)	200 mg BID
Weeks 9 and beyond	250 mg BID
(Cycle 3+)	

Table 3:Initial Recommended Phase 2 Dose

The two new dose schedules are designated as dose schedule 1 (DS1) and dose schedule 2 (DS2) are as follows:

Dose Schedule 1 (DS1)

	MS-553 Oral Daily Dose
Week 1	150 mg BID
Week 2	200 mg BID
Week 3 and beyond	250 mg BID

Dose Schedule 2 (DS2)

	MS-553 Oral Daily Dose
Cycle 1 and beyond	225 mg BID

Twenty of the 40 additional patients will be treated with DS1 and the other 20 patients with DS2. The patients will be allocated to either DS1 or DS2 in alternating fashion, according to the sequence of their enrollment. For example, the first enrolled patient will be allocated to DS1, the second patient to DS2, the third patient to DS1, the fourth to DS2, and so on.

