3.3.3. Dose Escalation: Combination Cohort B1

Once the MTD or initial RP2D is established for the monotherapy Cohort A1, enrollment in Cohort B1 will begin at 150 mg BID. The principles outlined in Section 3.3.2 will be followed for the Dose Escalation for the combination regimens. One or more 3+3 dose escalation cycles may be undertaken to determine an initial RP2D for MS-553 for each combination expansion cohorts. At least two dose levels are planned for Cohort B1. The dosing schedule and DLT evaluation periods are described in the table below.

Table 4. Dosing Schedule and DET Evaluation Tenous for Conort DI				
MS-553 Dose Levels	Dosing Schedule	DLT Evaluation Period		
150 mg BID	In 28-day cycles	Cycle 1		
200 mg BID	In 28-day cycles	Cycle 1		

Table 4: Dosing Schedule and DLT Evaluation Periods for Cohort B1

MTD determination, DLT and safety assessments will follow the general principles outlined in Cohort A1. Initial RP2D of MS-553 in the combination therapy is expected to be reached before the dose escalation reaches 250 mg BID, the high dose level of MS-553 monotherapy under testing. Intermediate dose levels (i.e. at 25 mg increment) or lower dose levels may also be evaluated as determined by the Investigators, the SRC and Sponsor until the MTD or initial RP2D for the combination is determined.

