3.3.4. Dose Escalation: Combination Cohort C1

Once the MTD or initial RP2D is established for the monotherapy (Cohort A1), enrollment in Cohort C1 will begin. Starting with cycle 1, patients will be dosed with MS-553 by mouth twice daily beginning at 150 mg BID, and rituximab will be started according to standard of care, and as outlined in Section 5.2.3.3. Beginning with Cycle 3, venetoclax dosing once daily by mouth will be initiated with weekly dose escalations from 20 mg to 400 mg over 5 weeks.

At least two dose levels are planned for Cohort C1. The dosing schedule and DLT evaluation periods are described in the table below.

Dose	Cycle 1	Cycle 2	Cycle 3	Cycle 4+	DLT
level					Period(s)
150 mg	150 mg	150 mg	150 mg	150 mg	Cycle 1
BID	BID	BID	BID	BID	through 4
200 mg	200 mg	200 mg	200 mg	200 mg	Cycle 1
BID	BID	BID	BID	BID	through 4

 Table 5:
 Dosing Schedule and DLT Evaluation Periods for Cohort C1

MTD determination, DLT and safety assessments will follow the general principles outlined in Cohort A1. Initial RP2D of MS-553 in the combination therapy is expected to be reached before or when the dose escalation reaches 250 mg BID, the high dose level of MS-553 under testing as monotherapy. Intermediate dose levels (i.e., at 25 mg increment) or lower dose levels may also be evaluated as determined by the Investigators, the Safety Review Committee and Sponsor until the MTD or initial RP2D for the combination is determined.

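### The one-cycle safety test for intra-patient escalation in Section 3.3.2 does not fit Cohort C1, where Cycle 1 contains no venetoclax and the DLT period is four cycles

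*Combined protocol and SAP*

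**What the plan says.** **The rule.** Section 3.3.2 is headed as general principles and names no cohort for intra-patient escalation. Criterion 1 has two parts. The first concerns experience at the new dose: "The next higher dose for the regimen has been demonstrated to be safe by at least 3 patients". The second sets the length of observation: "all 3 patients complete one cycle without experiencing any DLT". Criterion 2 asks that the patient has had no DLT and "has also completed at least 2 cycles of therapy at their current dose". Criterion 3 limits the move to one dose level. The step is discretionary and requires discussion with the medical monitor and Sponsor. The same section also words the cohort escalation trigger (3/3 or 5/6 patients without a DLT) and the acceptance of an MTD in terms of one 28-day cycle.

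**Its reach.** Section 3.3.3 states: "The principles outlined in Section 3.3.2 will be followed for the Dose Escalation for the combination regimens". The synopsis says the A1 and B1 dosing rules are applied similarly to C1. Section 3.3.4, on C1 itself, carries over less: "MTD determination, DLT and safety assessments will follow the general principles outlined in Cohort A1". In the synopsis, the statement that "intra-patient dose escalation will be permitted at the discretion of the study investigators" appears under Cohort A only.

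**Cohort C1.** Cycles 1 and 2 are MS-553 plus rituximab. Venetoclax starts in Cycle 3 and is ramped up over five weeks (Sections 3.3.4 and 5.2.3.3). The synopsis, under Cohort C2, explains that "the DLT evaluation period for the triplet combination is extended to 4 cycles of therapy" so that the ramp-up is included. Table 5 gives Cycles 1 through 4 as the DLT period at both planned levels. The synopsis sets the C1 cohort trigger and DLT evaluability at four cycles.

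**The concern.** The four-cycle DLT period exists because the first two cycles say nothing about the triplet. The intra-patient rule counts a dose as cleared after one cycle. In C1 that cycle is 28 of 112 days (25%) of the DLT period and contains no venetoclax.

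If a site and the sponsor take the rule to cover C1, a patient already on venetoclax can be raised to an MS-553 dose that nobody need yet have taken with venetoclax. That patient would be the first to receive the triplet at that dose, outside the cohort that is meant to establish its tolerability.

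**Working it through.** **Inputs**
- Cycle length: 28 days.
- C1 DLT period: Cycles 1 to 4 (synopsis; Table 5).
- Venetoclax start: Cycle 3, with a five-week ramp to 400 mg (Section 3.3.4).
- C1 cohort trigger: four cycles (synopsis, Cohort C1).
- Intra-patient criterion 1: one cycle in each of three patients. Criterion 2: two cycles at the current dose (Section 3.3.2).

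**The plan's own figures.** DLT period: 4 × 28 / 7 = 16 weeks, as the synopsis states. Time before venetoclax: 2 × 28 / 7 = 8 weeks, as Section 5.2.3.3 states.

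**Timeline.** Days are counted from the start of the 150 mg BID cohort. The assumptions are same-day starts within a cohort, the four-cycle cohort trigger, and no delay for committee review.
1. The 200 mg cohort opens at 4 × 28 = day 112.
2. Criterion 1 is met at 112 + 28 = day 140.
3. Criterion 2 was met at 2 × 28 = day 56, so it is not the limiting condition.
4. The 150 mg patient began venetoclax after day 56, and the ramp ended by 56 + 35 = day 91. On schedule, this patient is on 400 mg at day 140.
5. Patients in the 200 mg cohort start venetoclax at 112 + 56 = day 168, which is 168 − 140 = **28 days** after the move becomes possible.
6. Their DLT period ends at 112 + 112 = day 224, which is 224 − 140 = **84 days** after the move becomes possible.

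A committee review of any length before the 200 mg cohort opens shifts days 140, 168 and 224 equally and leaves both gaps unchanged.

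**Staggered accrual.** Let the third qualifying patient at the new dose start s days after the first. Measured from the first patient's start, criterion 1 is met at s + 28.
- No one in the new cohort on venetoclax: 56 − (s + 28) = 28 − s days, if s < 28.
- No one through the DLT period: 112 − (s + 28) = 84 − s days, if s < 84.
- Third patient's remaining DLT period: (s + 112) − (s + 28) = 84 days for every s.

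| s (days) | No venetoclax at new dose | No one through DLT period | Third patient's DLT period left |
|---|---|---|---|
| 0 | 28 | 84 | 84 |
| 14 | 14 | 70 | 84 |
| 28 | 0 | 56 | 84 |
| 56 | 0 | 28 | 84 |

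The documents do not give s, so the table shows a range. No DLT rate is assumed.

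**Cohort trigger.** For C1, Section 3.3.2 says one cycle where the synopsis trigger, the synopsis evaluability rule and Table 5 say four. Section 3.3.2 also disagrees with itself, because its evaluability rule already runs through the DLT period rather than one cycle.

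**The case against.** **The rule may not reach C1.** The synopsis places it under Cohort A, Section 3.3.4 imports a narrower list that omits it, the sentence in 3.3.3 sits in the B1 section, and Table 5 holds each C1 level constant from Cycle 1 onward. These points stand, and they make the reach contested. They do not settle it: 3.3.3 speaks of combination regimens in the plural, the synopsis applies the A1 and B1 dosing rules to C1, and no sentence excludes C1.

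**Criterion 1 also requires the dose to be shown safe for the regimen.** A careful reader could say that a cycle without venetoclax cannot show this for a triplet. That is fair, but the plan does not define the phrase, and the only stated duration is one cycle.

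**There are safeguards.** The step is discretionary, limited to one level, and discussed with the medical monitor and Sponsor. None of these sets a minimum amount of data. The Safety Review Committee's confirmation in 3.3.2 follows completion of a cohort and concerns escalation to the next level, not one patient's move.

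**Two stronger readings are tempting and are not supported.** A reader might infer from the one-cycle wording that C1 escalates its cohorts after a single cycle. The synopsis, Table 5 and the evaluability rules show that four cycles is intended. A reader might also infer from criterion 2 alone that a patient could move after two cycles, just as venetoclax begins. That ignores the four-cycle trigger, under which a patient from the cohort that opened the next level could move no earlier than about day 140. By then that patient has completed the whole triplet DLT period at the lower dose, which is a real mitigation.

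**Conclusion.** The point holds conditionally. The intra-patient rule has no four-cycle version anywhere, and the plan does not say whether it covers C1. If it does, the stated minimum allows a patient on full-dose venetoclax to move to 200 mg BID about 28 days before any patient in the 200 mg cohort takes venetoclax, and 84 days before that cohort's DLT period ends. Both figures assume same-day starts and the four-cycle cohort trigger. Staggered accrual shrinks the first gap to zero at s = 28 days, but the third patient always has 84 days of the DLT period left.

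The cohort and MTD trigger is a wording inconsistency, not a one-cycle design. The documents do not show that the plan positively authorises intra-patient escalation in C1, or that a higher MS-553 dose is unsafe with venetoclax. What they show is a dose-increase rule that sites could read in two ways, one of which bypasses the observation period the sponsor chose for the triplet. It should be corrected.

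**What to change.** In Section 3.3.2, replace the three fixed-length expressions with *the DLT evaluation period for the cohort*: the first-cycle wording, the 28-day-cycle wording in the escalation and MTD triggers, and the one-cycle wording in criterion 1. Alternatively, keep criterion 1 as it is and state that intra-patient escalation is not permitted in C1. In either case, restate the four-cycle 3/3 or 5/6 trigger in Section 3.3.4, where it is missing.

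The cost is wording only. A1 and B1 are unchanged because their DLT period is already one cycle (Section 3.3.1 and Table 4). No patients or visits are added, and cohort escalation takes no longer than now intended. The downside is that intra-patient escalation in C1 comes 112 − 28 = 84 days later, or not at all.

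A separate, minor alignment can be made in the same amendment. The synopsis ties the four-cycle period to doses up to 225 mg BID, while Section 3.3.4 expects the initial RP2D to be "reached before or when the dose escalation reaches 250 mg BID".

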3.3.3. Dose Escalation: Combination Cohort B1

Once the MTD or initial RP2D is established for the monotherapy Cohort A1, enrollment in Cohort B1 will begin at 150 mg BID. The principles outlined in Section 3.3.2 will be followed for the Dose Escalation for the combination regimens. One or more 3+3 dose escalation cycles may be undertaken to determine an initial RP2D for MS-553 for each combination expansion cohorts. At least two dose levels are planned for Cohort B1. The dosing schedule and DLT evaluation periods are described in the table below.

Table 4. Dosing Schedule and DET Evaluation Tenous for Conort DI				
MS-553 Dose Levels	Dosing Schedule	DLT Evaluation Period		
150 mg BID	In 28-day cycles	Cycle 1		
200 mg BID	In 28-day cycles	Cycle 1		

Table 4: Dosing Schedule and DLT Evaluation Periods for Cohort B1

MTD determination, DLT and safety assessments will follow the general principles outlined in Cohort A1. Initial RP2D of MS-553 in the combination therapy is expected to be reached before the dose escalation reaches 250 mg BID, the high dose level of MS-553 monotherapy under testing. Intermediate dose levels (i.e. at 25 mg increment) or lower dose levels may also be evaluated as determined by the Investigators, the SRC and Sponsor until the MTD or initial RP2D for the combination is determined.

3.3.4. Dose Escalation: Combination Cohort C1

Once the MTD or initial RP2D is established for the monotherapy (Cohort A1), enrollment in Cohort C1 will begin. Starting with cycle 1, patients will be dosed with MS-553 by mouth twice daily beginning at 150 mg BID, and rituximab will be started according to standard of care, and as outlined in Section 5.2.3.3. Beginning with Cycle 3, venetoclax dosing once daily by mouth will be initiated with weekly dose escalations from 20 mg to 400 mg over 5 weeks.

At least two dose levels are planned for Cohort C1. The dosing schedule and DLT evaluation periods are described in the table below.

Dose	Cycle 1	Cycle 2	Cycle 3	Cycle 4+	DLT
level					Period(s)
150 mg	150 mg	150 mg	150 mg	150 mg	Cycle 1
BID	BID	BID	BID	BID	through 4
200 mg	200 mg	200 mg	200 mg	200 mg	Cycle 1
BID	BID	BID	BID	BID	through 4

 Table 5:
 Dosing Schedule and DLT Evaluation Periods for Cohort C1

MTD determination, DLT and safety assessments will follow the general principles outlined in Cohort A1. Initial RP2D of MS-553 in the combination therapy is expected to be reached before or when the dose escalation reaches 250 mg BID, the high dose level of MS-553 under testing as monotherapy. Intermediate dose levels (i.e., at 25 mg increment) or lower dose levels may also be evaluated as determined by the Investigators, the Safety Review Committee and Sponsor until the MTD or initial RP2D for the combination is determined.

3.3.5. Dose Limiting Toxicity Definition

Dose limiting toxicities (DLT) occurring during DLT period appropriate for the cohort will be used to determine which dose of MS-553 will be examined in expansion cohorts. Toxicities will be assessed utilizing the National Cancer Institute Common Terminology Criteria for Adverse Events (NCI CTCAE v5.0) in Appendix 4.

Dose limiting toxicities (DLT) are defined as any of the following treatment-emergent events occurring from Cycle 1 Day 1 (after administration of MS-553) through the end of the DLT period (unless the event is determined to be unrelated to the drug):

- 1. Death
- 2. Hematologic toxicities:
 - Grade 4 neutropenia for \geq 7 days
 - Grade 3 febrile neutropenia: absolute neutrophil count (ANC) <1000/mm³ and single temperature >38.3°C (101°F) or a sustained temperature ≥38°C (100.4°F) for > 1 hour
 - Grade 4 thrombocytopenia \geq 14 days (patients with baseline platelet count of \geq 50 x 10⁹/L)
 - Grade 4 thrombocytopenia ≥ 28 days (patients with baseline platelet count < 50 x $10^9/L)$
 - \geq Grade 3 thrombocytopenia associated with \geq Grade 2 hemorrhage
 - New ≥ Grade 3 anemia requiring transfusion in a patient previously transfusionindependent.
- 3. Nonhematologic toxicities:
 - Any other ≥ Grade 3 toxicity not reversed to any one of the following three conditions in 7 days with appropriate intervention: a) baseline; b) ≤ Grade 1; or c) a status considered to be controlled by the Safety Review Committee (For example, isolated ≥ Grade 3 laboratory toxicity [e.g., electrolyte abnormalities] not associated with clinical signs or symptoms and is reversed to Grade 2 with appropriate intervention in 7 days is not considered a DLT.)
 - Any treatment-related adverse event (TEAE) requiring >25% of doses of scheduled study drug to be withheld during the DLT period.

All patients will continue to be monitored for approximately 30 days (+7 days) after treatment discontinuation for development of any late treatment emergent adverse events. Any such late adverse events will be considered in the determination of the MTD/initial RP2D and dose schedule to be taken forward into the expansion phase of the study.

3.4. Dose Expansion Cohorts

Dose expansion cohorts will be initiated after determination of the MTD or initial RP2D for monotherapy or combination treatment.

3.4.1. Expansion Cohort A2: Monotherapy

A dose expansion cohort ("**expansion cohort A2**") of approximately 25 patients with refractory or relapsed CLL/SLL who (a) have failed at least two prior lines of therapies, or (b) have either acquired clinical and/or molecular (e.g., BTK and/or PLCG2 mutation) resistance to a BTK inhibitor after achieving an initial response will be activated, and enrolled at the initial RP2D or the highest dose level at which fewer than 2/6 patients have completed the first cycle without experiencing DLT (e.g., the MTD).

